6.4 Withdrawal of individual participants

Participants can leave the study at any time for any reason if they wish to do so without any consequences.

6.5 Replacement of individual subjects after withdrawal

Participants that left the study will not be replaced.

7. SAFETY REPORTING

7.1 Temporary halt for reasons of participant safety

In accordance with section 10, subsection 4, of the WMO, the sponsor will suspend the study if there is sufficient ground that continuation of the study will jeopardise participants health or safety. The sponsor will notify the accredited METC (Medical research ethics committee (MREC); in Dutch: medisch-ethische toetsingscommissie (METC)) without undue delay of a temporary halt including the reason for such an action. The study will be suspended pending a further positive decision by the accredited METC. The investigator will take care that all participants are kept informed.

7.2 AEs and SAEs

7.2.1 Adverse events (AEs)

Adverse events are defined as any undesirable experience occurring to a participant during the study visit, whether or not considered related to trial procedure. Only adverse events during the visit will be considered and reported as (serious) adverse events.

7.2.2 Serious adverse events (SAEs)

A serious adverse event is any untoward medical occurrence or effect that:

- results in death;
- is life threatening (at the time of the event);
- requires hospitalisation or prolongation of existing inpatients' hospitalisation;
- results in persistent or significant disability or incapacity;
- is a congenital anomaly or birth defect; or
- any other important medical event that did not result in any of the outcomes listed above due to medical or surgical intervention but could have been based upon appropriate judgement by the investigator.

An elective hospital admission will not be considered as a serious adverse event.

Only SAEs occurring during or directly after the visit will be considered and reported as SAEs.

The investigator will report all SAEs to the sponsor without undue delay after obtaining knowledge of the events, except for the following SAEs:

• Events related to the indication of the Asthma/COPD consultation and not related to the SCOOP procedures performed during the visit, as interpreted by the investigator.

The sponsor will report the SAEs through the web portal *ToetsingOnline* to the accredited METC that approved the protocol, within 7 days of first knowledge for SAEs that result in death or are life threatening followed by a period of maximum of 8 days to complete the initial preliminary report. All other SAEs will be reported in line listings after study closure.

8. STATISTICAL ANALYSIS

The statistical analysis plan will be finalized prior to database lock and will include a more technical and detailed description of the statistical analyses described in this section. This section serves as a summary of the planned statistical analysis and the most important endpoints.

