6.2 Study procedures

Participants will be invited by the study site for a diagnostic or control visit to perform a lung function test. Together with the invitation for this visit, information about the SCOOP study is sent. The recipient will have the option to make their interest or disinterest in the study known before their visit (but this is not required). The study flow is presented in document E₃.

During the regular diagnostic or control visit participants that did not reply to the initial information and participants that have shared their interest will be further informed about the SCOOP study and asked whether they would like to participate. In case a person does not want to participate in the study, the Asthma/COPD visit will continue as usual. In case a person does want to participate in the study, the study activities will be added to the regular visit.

After signing informed consent, the visit will include a (pre-)oscillometry measurement followed by a (pre-)spirometry measurement. In case of a diagnostic visit the participant will use Salbutamol followed by a post-oscillometry and post-spirometry measurement after a 15-minute wait time. During the wait time, or after the measurements in case of a control visit, the participant is asked to fill in the SADT-c questionnaire and two additional study questions.

10-15 participants with a triage diagnosis of COPD and SAD status defined as R5–R20 > ULN will be invited for a cognitive interview regarding the new SADT-c questionnaire. Purposeful sampling will be used, to have a widespread of patient characteristics. If new items are added to the SADT-c questionnaire as a result of the cognitive interviews, 100 COPD patients that had previously completed the SADT-c questionnaire will be asked to complete the updated questionnaire.

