8.1 Primary study parameter(s)

The primary endpoint is the predictive value of SADT-c for SAD in COPD. The statistical hypothesis for the primary objective is that the predictive value of SADT-c is above the lower limit of the confidence interval of predictive value of SADT-a (AUC 0.74, LR+ 2.3 for the SADT-a bronze model). The hypothesis will be tested at a 2-sided significance level of 0.05.

For the analysis of this primary endpoint, the following population is defined:

- All participants that have a prior or novel COPD (triage) diagnosis, and
- Do not have an asthma, asthma-COPD overlap syndrome, missing or other diagnosis, and
- Have filled in the SADT-c questionnaire.

The presence of SAD will be based on oscillometry results. A resistance difference between 5 and 20 Hz (R5-R20) cutoff of 0.07 kPa x s x L⁻¹ will be used to define the presence of SAD¹⁵.

Analysis will be performed as done earlier for the development of SADT for asthma⁸. In short, to assess the predictive value of SADT-c we first will select the most important SADT items (secondary study parameter). Regression analysis will be used to select SADT items that show a relation with SAD in the expected direction based on the content validity of the items. In a next step the most important SADT items for SAD group will be selected by using logistic regression models. Prediction models using bootstrapping resampling will be used. In addition to the individual SADT items, also patient characteristics, such as age, sex, and height, BMI, will be considered as independent predictors in the model.

Selected key SADT items will be used together with available clinical information to build logistic regression models to predict the SAD group. Three levels of clinical information will be considered resulting in three regression models:

- Bronze: Basic patient characteristics (such as age, sex, age at diagnosis, BMI, or other)
- Silver: Spirometry test results (FEV₁ % predicted)
- Gold: Oscillometry test results (R5-R20 and reactance area (AX)).

For each model the area under the receiver operating characteristic curve (AUC), positive likelihood ratio (LR+) and sensitivity and specificity will be calculated, using a probability cut-off of 0.5 to indicate predicted SAD.

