8.2 Secondary study parameter(s)

SADT-c

To determine whether bronze model SADT-a is predictive for SAD in COPD, the steps described in section 8.1 will be followed. The AUC, LR+ and sensitivity and specificity will be calculated and reported.

To assess the agreement between SADT-c and disease parameters, the steps described in section 8.1 will be reported. Logistic regression analysis results will be reported.

To assess the content validity and reliability of the SADT-c, 10-15 patients with COPD and SAD will be invited for a cognitive interview. Results will be presented in a descriptive way.

To evaluate how SADT-c and SADT-a compare in detecting SAD in COPD the predictive values of the various SADT-c and SADT-a models will be compared.

In case the SADT-c has a significantly reduced predictive value as compared to the SADT-a, new items derived from the cognitive interviews will be added, if any. The amended questionnaire will subsequently be reinvestigated using the same protocol, in the same population (ie. 100 patients with COPD participating in the SCOOP study).

Oscillometry vs spirometry

To assess the agreement between oscillometry and spirometry, triage diagnoses as determined by the expert panel will be compared. Cohen's kappa or comparable statistics will be used to compare the outcomes. Additional analysis will be done adjusted for difficulty of diagnosis and the agreement between panel members. In addition, subgroup analysis will be performed based on the level of agreement between panel members.

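### The SAP deadline is database lock, but the 8.2 amendment decision uses the primary endpoint and may precede lock, so open analysis rules could be settled after the result is known

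*Protocol*

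**What the plan says.** Section 8 gives one deadline for the SAP: "The statistical analysis plan will be finalized prior to database lock". It does not tie that deadline to first data access or to the first model fit, and no second or staged lock is mentioned.

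Section 8.1 defines the primary endpoint: "The primary endpoint is the predictive value of SADT-c for SAD in COPD".

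Section 8.2 makes an amendment depend on the same quantity: "In case the SADT-c has a significantly reduced predictive value as compared to the SADT-a, new items derived from the cognitive interviews will be added", provided the interviews yielded any. Then: "The amended questionnaire will subsequently be reinvestigated using the same protocol, in the same population", which the section identifies as the 100 patients with COPD in this study.

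Section 6.2 describes the amendment differently. Its condition is "If new items are added to the SADT-c questionnaire as a result of the cognitive interviews", and its consequence is that "100 COPD patients that had previously completed the SADT-c questionnaire will be asked to complete the updated questionnaire". Section 3 likewise makes the second completion depend on whether the interviews show a need for more questions. Neither section mentions predictive value.

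**The concern.** Finalising a SAP before database lock protects the primary analysis as long as nobody has analysed the outcome by then. Section 8.2 puts that condition in doubt. To find out whether SADT-c is significantly worse than SADT-a, the team must link the answers to SAD status, select items, fit models and compare them. If the answer is yes and new items exist, data collection continues. With a single lock at the end, the first primary result comes before lock, and the stated deadline lets the SAP be completed afterwards.

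At stake is the value of having a primary hypothesis fixed in advance. Choices that section 8.1 leaves open could be made, even unintentionally, by people who know which choice meets the hypothesis.

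**Working it through.** **Step 1. Order of events under 8.2 with one lock**
1. Visit data and first questionnaire are collected (sections 3, 6.2).
2. SADT-c predictive value is estimated and compared with SADT-a (8.1, 8.2).
3. If it is significantly reduced and the interviews gave new items, the questionnaire is amended (8.2).
4. The same patients complete the amended form (6.2, 8.2).
5. The analysis is repeated (8.2).
6. Database lock; the SAP must be final by now (8).

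The stated deadline is at step 6, and the primary endpoint is first known at step 2.

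**Step 2. What 8.1 fixes and what it leaves open**
- Fixed: analysis population, two-sided 0.05, probability cut-off 0.5, an R5-R20 cut-off of 0.07, logistic regression with bootstrapping, and an expected-direction filter for items.
- Open: which of the three models carries the primary test (bronze figures appear only in parentheses); whether AUC or LR+ decides; the pass mark, described as the SADT-a lower confidence limit but given only as point estimates (0.74 and 2.3); the bronze predictor list, which is open-ended; the number of items and the threshold for keeping them; the test behind the 8.2 comparison; and whether the first or the amended form carries the hypothesis.

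**Step 3. Does the rerun itself inflate the error?**
Assumptions, none of them in the protocol: Z1 and Z2 are standard normal test statistics for the first and amended forms with correlation rho, and the upper-tail critical value is 1.96 (nominal 0.025). A rerun happens only if Z1 < t. New items are assumed always to be available, which is the worst case.

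Upper-tail error = 0.025 + P(Z1 < t and Z2 > 1.96).

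| t | rho 0.5 | rho 0.7 | rho 0.9 |
|---|---|---|---|
| -1.96 | 0.0250 | 0.0250 | 0.0250 |
| -1.23 | 0.0251 | 0.0250 | 0.0250 |
| -0.90 | 0.0252 | 0.0250 | 0.0250 |

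A form that has just done clearly badly rarely passes by chance on a correlated retest. If instead a rerun followed any non-success, the error would be 1 - P(Z1 <= 1.96 and Z2 <= 1.96), which is 0.042 at rho 0.7 and 0.035 at rho 0.9. Section 8.2 does not permit that.

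**Step 4. Illustration of free choice (not an effect of the trigger)**
If the best of k equicorrelated tests could be chosen freely, the error is 1 - P(all k <= 1.96). For rho from 0.9 to 0.5:
- k = 2: 0.035 to 0.045
- k = 4: 0.047 to 0.078
- k = 6: 0.054 to 0.104

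Both k and rho are assumed.

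**Step 5. Could analytic choices matter at this sample size?**
Inputs: 100 patients with COPD and SAD prevalence 74% to 83% (4.4); AUC 0.74 (8.1). Hanley-McNeil, with m patients with SAD and n without:

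SE = sqrt{[A(1-A) + (m-1)(Q1-A²) + (n-1)(Q2-A²)] / (mn)}, where Q1 = A/(2-A) = 0.587 and Q2 = 2A²/(1+A) = 0.629.

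- 74/26: sqrt[(0.192 + 2.898 + 2.046)/1924] = 0.052; 95% interval 0.64 to 0.84.
- 83/17: sqrt[(0.192 + 3.256 + 1.309)/1411] = 0.058; 95% interval 0.63 to 0.85.

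With intervals about 0.2 wide, modest changes in items, predictors or pass mark could decide whether the hypothesis or the trigger is met.

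**The case against.** - **Common practice.** SAP sign-off before lock is normal and would be no fault alone. This stands; the difficulty lies only in its combination with a result-dependent amendment.
- **Timing is inferred.** Section 8.2 gives no timing relative to lock. Section 3 describes a single visit at which all data are collected, so a lock of the visit data, the 8.1 analysis, and a second stage with its own lock would fit the text. This also stands: the protocol permits the unsafe order but does not prescribe it. Nor does it state the safe one.
- **The exposure is conditional.** More data are collected under 8.2 only if SADT-c is significantly worse and new items exist. Under the trigger in sections 3 and 6.2, no look at predictive value is needed to decide on an amendment. Both are correct. They limit the point and expose a disagreement between sections.
- **Much of 8.1 is already fixed.** True for the items in step 2. The SAD definition has a separate problem: 8.1 uses 0.07, while 6.1.1, 6.1.2 and 6.2 use the upper limit of normal. That is a contradiction to resolve in its own right.

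A reader might infer that the 8.2 trigger raises the false-positive rate to 3.5-10%. The documents do not support this. That range describes free choice among 2 to 6 analyses under assumed correlations; the rerun that 8.2 allows leaves the error at about 0.025. The multiplicity of models and metrics also exists whatever the SAP date. Nor do the documents show that the SAP will in fact be written after the result.

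**Conclusion.** The point holds as a gap in timing. The stated deadline permits the SAP to be finalised after the primary result is known, because the 8.2 decision uses the primary endpoint and may be followed by further data collection. This rests on the 8.2 trigger being the operative one and on there being a single lock; the protocol mentions no other.

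The rerun contributes essentially nothing to type I error (0.0250 to 0.0252 against 0.025, for assumed correlations of 0.5 to 0.9). The remaining risk is result-driven choice among the open elements. Its size cannot be derived from the protocol, and the step 4 figures only illustrate it. No sample size or other stated figure changes. The amendment is a modest, inexpensive improvement and does not call the design into question.

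**What to change.** 1. In section 8, replace the lock-based deadline: the SAP is finalised and dated before SADT-c answers are first analysed against SAD status, and in any case before the 8.2 comparison. It should settle the SAD definition, item-selection rule, predictor list, primary model, deciding metric, pass mark, and the test behind the amendment trigger. If staged locks are intended, state the lock points.
2. State in 8.1 or 8.2 which questionnaire version carries the primary test, and label the analysis of the other as exploratory.
3. Reconcile the interview-based trigger in sections 3 and 6.2 with the result-based trigger in 8.2.

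The cost is earlier sign-off of a document already promised. No extra patients, visits or measurements are needed.

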8.1 Primary study parameter(s)

The primary endpoint is the predictive value of SADT-c for SAD in COPD. The statistical hypothesis for the primary objective is that the predictive value of SADT-c is above the lower limit of the confidence interval of predictive value of SADT-a (AUC 0.74, LR+ 2.3 for the SADT-a bronze model). The hypothesis will be tested at a 2-sided significance level of 0.05.

For the analysis of this primary endpoint, the following population is defined:

- All participants that have a prior or novel COPD (triage) diagnosis, and
- Do not have an asthma, asthma-COPD overlap syndrome, missing or other diagnosis, and
- Have filled in the SADT-c questionnaire.

The presence of SAD will be based on oscillometry results. A resistance difference between 5 and 20 Hz (R5-R20) cutoff of 0.07 kPa x s x L⁻¹ will be used to define the presence of SAD¹⁵.

Analysis will be performed as done earlier for the development of SADT for asthma⁸. In short, to assess the predictive value of SADT-c we first will select the most important SADT items (secondary study parameter). Regression analysis will be used to select SADT items that show a relation with SAD in the expected direction based on the content validity of the items. In a next step the most important SADT items for SAD group will be selected by using logistic regression models. Prediction models using bootstrapping resampling will be used. In addition to the individual SADT items, also patient characteristics, such as age, sex, and height, BMI, will be considered as independent predictors in the model.

Selected key SADT items will be used together with available clinical information to build logistic regression models to predict the SAD group. Three levels of clinical information will be considered resulting in three regression models:

- Bronze: Basic patient characteristics (such as age, sex, age at diagnosis, BMI, or other)
- Silver: Spirometry test results (FEV₁ % predicted)
- Gold: Oscillometry test results (R5-R20 and reactance area (AX)).

For each model the area under the receiver operating characteristic curve (AUC), positive likelihood ratio (LR+) and sensitivity and specificity will be calculated, using a probability cut-off of 0.5 to indicate predicted SAD.

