The SADT-a predicts SAD in patients with asthma using a single criterion – wheezing at rest – along with certain basic patient characteristics, such as age, sex, age at diagnosis, and Body Mass Index (BMI); this is the bronze model (area under receiver operation characteristic curve (AUC) 0.74 and positive likelihood ratio (LR+) 2.3). Its ability to accurately identify SAD in asthma is greatly enhanced with the use of spirometry, which evaluates lung function by measuring air volume and flow during breathing; this represents the silver model (AUC 0.87, LR+ 5.0). The results from spirometry primarily include the FEV_1 % predicted. The diagnostic precision further improves with the incorporation of oscillometry, marking the gold model (AUC 0.96, LR+ 12.8). This technique assesses lung function by measuring airflow resistance and includes parameters like the resistance difference between 5 and 20 Hz (R5-R20) and reactance area (AX)⁸.

The current study aims to adapt the original 63-item SADT questionnaire for dedicated use in COPD by reducing the number of items and enhance its efficiency in identifying SAD in individuals with COPD (the SADT-c). This process will follow the approach previously used for asthma⁸. We will assess the predictive value of SADT-c. Additionally, we will determine whether the bronze model of SADT-a is similarly predictive for SAD in COPD as is the bronze model of SADT-c.

Since oscillometry is not standardized in clinical practice, and the access and quality of spirometry is low¹¹, it would be of great value to determine whether oscillometry and spirometry are equally effective in the diagnostic work-up of respiratory symptomatic patients in primary care. Spirometry requires collaboration of the patient to perform a forced expiratory maneuver and well-trained Version 1.0, 19 April 2024 9 of 27

staff¹², whereas oscillometry is easy to perform as no training and limited effort of the patient is required (45 seconds of tidal breathing) and limited training of the staff¹³. In order to compare the effectiveness of spirometry and oscillometry, spirometry and oscillometry measurement will be interpreted by a panel of experts to provide a triage diagnosis. The previously developed machine learning AC/DC tool will be used to explore its diagnostic accuracy using oscillometry and spirometry results¹⁴.

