6. METHODS

6.1 Study endpoints

6.1.1 Main study endpoint

The primary endpoint is the predictive value of SADT-c for detecting SAD in patients with COPD.

Required variables:

- Diagnosis of Asthma/COPD service
- SAD status defined as R5–R20 > upper limit of normal (ULN)¹
- SADT question results
- Patient characteristics
 - o Age
 - o Sex
 - o Height
 - Body Mass Index (BMI)
 - Age at diagnosis
- Oscillometry and spirometry results

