6.1.2 Secondary study endpoints

The secondary endpoints are:

- 1. Predictive value of SADT-a bronze model for SAD in COPD.
- 2. Agreement between SADT-c results and disease parameters.
- 3. Content validity and reliability.
- 4. Relative predictive value of SADT-a versus SADT-c for SAD in COPD defined as R5– R20 > ULN¹
- 5. Agreement between triage diagnoses from oscillometry and spirometry.
- 6. Relative usability of spirometry and oscillometry.

Required variables:

- 1.
- Triage diagnosis of Asthma/COPD service
- SAD status based on oscillometry test (R5-R20)
- SADT question 8
- Patient characteristics (bronze model)
 - o Age
 - o Sex
 - o Height
 - o Body Mass Index (BMI)
 - Age at diagnosis
- 2.
- Triage diagnosis by Asthma/COPD service
- SAD status based on oscillometry test (R5-R20)
- Lung function results

- Asthma/COPD service collected questionnaires and patient characteristics (as described in chapter 5)
- SADT-c variables
- Patient characteristics bronze model
- 3.
- Cognitive interviews
- SADT-c results
- 4.
- Predictive value SADT-a different models
- Predictive value SADT-c different models
- 5.
- Panel expert diagnoses (spirometry)
- Panel expert diagnoses (oscillometry)
- Patient characteristics
- Difficulty to diagnose (scale)
- 6.
- Operator opinion
- Expert interpreter opinion
- Duration of measurement
- Patient burden

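### The asthma LR+ of 2.3 does not carry over to COPD as part of the primary bar, and the AUC part is only an external performance goal that cannot show how SADT-c performs relative to SADT-a

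*Protocol*

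**What the plan says.** - **Primary hypothesis (Protocol 8.1).** The claim put to the test reads: "the predictive value of SADT-c is above the lower limit of the confidence interval of predictive value of SADT-a (AUC 0.74, LR+ 2.3"). Both figures in brackets are those of the bronze version. On the error level, the section adds: "The hypothesis will be tested at a 2-sided significance level of 0.05". The lower limit itself is not given, for AUC or for LR+.
- **Origin of the figures (Protocol 1).** They describe asthma: "The SADT-a predicts SAD in patients with asthma using a single criterion" plus basic patient characteristics.
- **Outcome.** In 8.1 an R5-R20 "cutoff of 0.07 kPa x s x L⁻¹ will be used to define the presence of SAD". Section 6.1.1 has "SAD status defined as R5–R20 > upper limit of normal (ULN"). How SAD was defined when SADT-a was developed is not stated anywhere.
- **Gold model in asthma (Protocol 1).** R5-R20 is among its predictors. "The diagnostic precision further improves with the incorporation of oscillometry, marking the gold model (AUC 0.96, LR+ 12.8").
- **Classification (Protocol 8.1).** AUC, LR+, sensitivity and specificity are calculated for each model. A predicted probability of 0.5 is the threshold for calling SAD.
- **Prevalence and size (Protocol 4.4).** SAD is expected in 74% to 83% of COPD patients, and 100 such patients are planned.
- **Comparison in COPD.** Section 6.1.2 lists "Predictive value of SADT-a bronze model for SAD in COPD" as a secondary endpoint, and the relative value of SADT-a and SADT-c as another. Section 8.2 plans to compare the models. It also provides for adding items if SADT-c is significantly worse than SADT-a, without saying whether the asthma or the COPD figure for SADT-a applies.

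**The concern.** A bar taken from another study is fair only if the measure would take about the same value here for an equally good tool. Three things differ or may differ between the source of the bar and this trial: the disease, the definition of SAD and the share of patients who have SAD.

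The third matters most for LR+. When a calibrated model is cut at a fixed probability of 0.5, the point on the ROC curve at which it operates depends on prevalence. LR+ therefore moves with prevalence even when discrimination does not change.

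Two conclusions are at stake. SADT-c could be declared worse than SADT-a when it discriminates equally well. And the step in 8.2 that adds items and asks about 100 patients to complete a new questionnaire could be set off by a difference in prevalence and not by a weakness of the tool.

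**Working it through.** **1. Can LR+ 2.3 be used as a bar at these settings?**

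Inputs: AUC 0.74 and LR+ 2.3 (Protocol 1 and 8.1), probability cut-off 0.5 (8.1), SAD prevalence p of 74% to 83% (4.4). Assumption: the score is calibrated and binormal with equal variances, N(0,1) without SAD and N(d,1) with SAD.

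- Separation: d = √2 × Φ⁻¹(0.74) = 0.910.
- Score at which the predicted probability is 0.5: t = [d²/2 − ln(p/(1−p))]/d.
- Sensitivity = 1 − Φ(t − d), false-positive rate = 1 − Φ(t), LR+ = sensitivity / false-positive rate.

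At p = 0.74: t = (0.414 − 1.046)/0.910 = −0.695. Sensitivity is 0.946, the false-positive rate is 0.756 (specificity 0.244), and LR+ = 0.946/0.756 = 1.25.

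At p = 0.83: t = (0.414 − 1.586)/0.910 = −1.288. Sensitivity is 0.986, the false-positive rate is 0.901 (specificity 0.099), and LR+ = 0.986/0.901 = 1.09.

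The same tool, AUC 0.74 throughout:

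| SAD prevalence | LR+ at cut-off 0.5 |
|---|---|
| 30% | 3.83 |
| 40% | 2.74 |
| 50% | 2.08 |
| 60% | 1.64 |
| 74% | 1.25 |
| 83% | 1.09 |

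The prevalence in the asthma study is not in the protocol, so its 2.3 cannot be reproduced directly. In this model 2.3 falls between the values for 40% and 50%. Solving the same equations for LR+ = 2.3 gives a required AUC of about 0.89 at 74% prevalence (0.929/0.404) and 0.92 at 83% (0.964/0.419). An LR+ of 2.3 in this COPD population is thus a far harder demand than an AUC of 0.74.

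**2. Was the asthma outcome the same as the one in 8.1?**

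If SAD is R5-R20 above a fixed 0.07, then R5-R20 separates the two groups completely, and a model that includes the same reading can reach AUC 1.00. Simulation confirms 1.00. The asthma gold model, which includes R5-R20, is reported at 0.96 with LR+ 12.8. The same reading against a fixed cut-off does not fit those figures.

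The inference weakens if a patient-specific upper limit of normal was used. With simulated limits, the AUC of R5-R20 alone is about 0.997, 0.99, 0.975, 0.96 and 0.94 when the SD of the limit is 0.1, 0.2, 0.3, 0.4 and 0.5 times the SD of R5-R20. With age, sex and BMI also in the model, it was 0.995 and 0.983 in two assumed scenarios. So 0.96 is possible under strong variation. It is also possible if predictor and outcome came from different readings, for example before and after bronchodilation.

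**The case against.** The strongest reply is that the primary objective asks whether SADT-c can be used in COPD, not whether it beats SADT-a there. The second question has its own objective, endpoint and planned comparison. The Summary and section 9.3 frame the aim as doing in COPD what SADT-a does in asthma, so an external goal taken from asthma follows from the stated purpose. This stands for the AUC. It does not rescue the LR+, because at the stated cut-off and prevalence an equally discriminating tool would not reproduce 2.3.

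Three stronger readings are tempting, and the protocol does not support them.

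- *That its figures prove a different SAD definition in asthma.* They make it probable. The definition is not stated, and a varying upper limit of normal or a different reading could explain 0.96.
- *That the AUC bar inflates the false-positive rate whenever SADT-a would do better in COPD than in asthma.* The bar is a lower confidence limit. A tool whose true AUC lies above it passes correctly, and how often it does so is power, not error.
- *That the primary test should become non-inferiority to SADT-a in COPD.* If SADT-a performs badly in COPD, a poor SADT-c could pass. No margin is available, and SADT-c is built on the same patients. That is a debatable trade, not a correction.

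**Conclusion.** The point holds in a limited form. The asthma origin of the bar is explicit. A different SAD definition is a reasonable inference and no more.

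The LR+ component is wrong as written: a tool with AUC exactly 0.74 would show about 1.25 at 74% prevalence and 1.09 at 83%, against a cited 2.3. This rests on a calibrated equal-variance binormal score and on the prevalence range in 4.4. Because the lower limit of 2.3 is not given, it cannot be said for certain that such a tool would miss the bar. In this model its expected LR+ lies below any limit above 1.25.

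The AUC component is usable as an external performance goal. How far an AUC in this COPD population would differ from the asthma value for an equally good tool, and in which direction, cannot be found from the protocol. Passing or failing it therefore supports no statement about SADT-c relative to SADT-a.

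**What to change.** In section 8.1:

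1. Remove LR+ 2.3 from the hypothesis. Report LR+ descriptively and quote the asthma value as context, with a sentence saying that LR+ at a fixed 0.5 cut-off depends on prevalence.
2. State the AUC bar as a fixed number, and say that it comes from another disease and possibly from another SAD definition.

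In section 8.2:

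3. Base any statement relative to SADT-a on the paired difference in AUC, SADT-c bronze minus SADT-a bronze, in the same COPD patients and against one R5-R20 outcome. The 0.07 cut-off in 8.1 and the upper limit of normal in 6.1.1 and 6.1.2 must be reconciled first.
4. Give that difference a bootstrap confidence interval that repeats item selection in every resample. SADT-c is selected and fitted on these patients, so an interval without that step would favour it.
5. Name this paired difference as the trigger for adding items.

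The cost is a change of wording and one paired analysis. The variables are already required for the secondary endpoints. What is lost is the LR+ test against the asthma figure.
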